$$n = \frac{2\sigma^2(z_{1-\alpha} + z_{1-\beta})^2}{(\mu_1 - \mu_2)^2}$$

Where,

n = Sample size = 60

σ = Population standard deviation = 9.2245

σ^2 = Variance = 85.0914

$Z_{1-\alpha}$ = Confidence level 95% = 1.96

$Z_{1-\beta}$ = Power of test = 95%

μ_1 = Population mean Group A = 67.73

μ_2 = Population mean Group B = 75.73

A total sample size of 60 patients (30 patients in each group) is estimated by using 5% level of significance and 95% power of test with expected mean value time to pass flatus in Group A (Chewing Gum) as was 67.73 ± 8.481 hours and Group B (Honey) as 75.73 ± 9.968 hours in the pilot study.

Sampling Technique: Non-probability purposive sampling. Patients admitted to the hospital for stoma reversal procedure will be assigned into Group A or B using a lottery method, ensuring that the sample population is divided into the two groups equally and randomly regardless of their characteristics (33).

Sample Selection:

Inclusion Criteria:

- All patients of age more than 18 years with an Ileostomy
- Undergoing surgery involving reversal of an Ileostomy i.e., Loop Ileostomy, Double Barrel Ileostomy, Ileocolostomy or End Ileostomy
- Time from fashioning of ileostomy to its reversal is of a duration greater than 1 month

Exclusion Criteria:

- Patients with existing complications as mentioned above in the operative definition of postoperative complications
- Patients with malignancy
- Patients with inflammatory bowel disease
- Patients who cannot communicate well
- Patients who have difficulty chewing or swallowing
- Patients who are prohibited from oral intake by the surgeon
- Patients having undergone Ileostomy reversal more than 1 day before being included in the study

Outcome Measures:

- Primary Outcome
 - Time to pass flatus
- Co-primary Outcomes
 - Time to bowel sounds
 - Time to pass feces
- Secondary Outcomes

- Time to full feeds
- Postoperative pain
- Postoperative nausea and vomiting
- Length of postoperative stay /Time to discharge

Data Collection Procedure:

After the approval to carry out this study from the Research Evaluation Unit (REU) College of Physicians and Surgeons Pakistan and the Institutional Review Board (IRB) King Edward Medical University, subjects meeting the operational definitions and the inclusion & exclusion criteria will be enrolled in the study after informed consent.

Randomization:

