Allocation: Patients will be randomly allocated in group A or B: A for the Oral Chewing Gum group and B for the Oral Honey group using the lottery method by the principal investigator.

Sequence Generation: The lottery method is a simple form of simple randomization used to assign participants into the two groups in a way that ensures unbiased allocation. Each participant will be assigned a case number from 1 onwards based on their induction into the study by the principal investigator. 30 identical paper slips will be made and Group A will be written in 15 slips and Group B will be written on the other 15 slips. The slips will be folded to conceal the written text. The slips will be mixed thoroughly and drawn randomly, and the participants will be assigned to a group based on the identifier on the slip, i.e. either Group A (chewing gum) or Group B (honey).

Concealment: The identifier “Group A” or “Group B” will be written on identical slips of paper and the slips will be folded to conceal the written text, ensuring blinding by making them indistinguishable.

Implementation:

The random allocation will be done by the principal investigator. The participants presenting to the out-patient clinic for ileostomy reversal will be admitted to the ward and enrolled into the study after fulfilling the inclusion criteria and passing the exclusion criteria by the principal investigator.

After a period of 24 hours from the ileostomy reversal surgery, the patients will be asked to start early water sips intake according to the ERAS protocol (6). Group A patients will be asked to chew gum for 5 minutes every 4 hours. Group B patients will be asked to eat one half tablespoon of natural honey every 4 hours. The outcome parameters will be assessed and

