documented every 8 hours in the case report form by the doctor on duty in the ward. As the data collection schedule will be 8 hourly, the doctor on duty in the ward for each day will be responsible for data collection. The doctors on duty in the ward will be trained by the principal investigator about the data collection procedure. The bowel sounds will be auscultated using a stethoscope placed on the right iliac fossa of the patient's abdomen. The patients will be questioned about whether they have passed flatus and feces and at what time they did so. The patients will be questioned about their last time taking full feeds, nausea, vomiting episodes. A visual analog scale for pain will be used to assess the pain score from 0 to 10 i.e. from no pain to the worst possible pain, subjective to each patient. The postoperative antibiotic, IV fluid, analgesic and PPI regimen will be standardized across the study participants. Relevant investigations to confirm the presence of complications will be carried out. All this information will be recorded in the case report form (attached).

Blinding: Selection bias will be addressed by randomly assigning the participants to the groups. Performance bias could not be eliminated due to different surgeons performing the ileostomy reversal surgery. Detection bias will be addressed by keeping the participants unaware of what group they are assigned to and because of the objective nature of the outcome variables. There will still be some detection bias in some respects involving the subjective opinion of the participants e.g. pain score. Intention-to-treat analysis will be done to address attrition bias.

Follow-up: The primary and secondary outcomes will be assessed at 8 hourly intervals after starting either oral chewing gum or honey 24 hours postoperatively and the data will be written manually in the case report form. The final assessment point will be till the time of discharge or a maximum of 5 days/144 hours postoperatively. Data collection will be concluded when the patients will be discharged by the consultant orders in the ward round. Oral chewing gum or honey intake will be stopped on discharge and the patients will be recommended to continue taking oral meals at home. Further follow-up will be not done after the patients are discharged from the hospital.

Data Analysis Procedure:

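### One person judges eligibility, enrols and allocates using unsealed folded slips from a fixed equal pool, so allocation is not concealed from the enroller and the claim that selection bias is addressed is not supported

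*Combined protocol and SAP*

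**What the plan says.** All of this is in the combined protocol and SAP.

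- **Who enrols.** Under Randomization, Implementation, patients are "enrolled into the study after fulfilling the inclusion criteria and passing the exclusion criteria by the principal investigator". Under Sequence Generation, "Each participant will be assigned a case number from 1 onwards based on their induction into the study by the principal investigator".
- **Who allocates.** The same person. Allocation says so, and Implementation repeats it: "The random allocation will be done by the principal investigator".
- **The pool.** Sequence Generation: "30 identical paper slips will be made and Group A will be written in 15 slips and Group B will be written on the other" (that is, an equal number for each group). The section calls this simple randomization and says that it gives unbiased assignment.
- **Concealment.** The whole measure is that "the slips will be folded to conceal the written text, ensuring blinding by making them indistinguishable".
- **Equal groups.** The Sampling Technique paragraph describes the lottery as "ensuring that the sample population is divided into the two groups equally and randomly regardless of their characteristics".
- **Recruitment.** "Sampling Technique: Non-probability purposive sampling". No person is named as the selector, and enrolment is not said to be consecutive.
- **The claim.** Under Blinding: "Selection bias will be addressed by randomly assigning the participants to the groups".

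**The concern.** A random draw and concealment of the coming assignment from the person who enrols are two separate protections. The plan supplies the first and treats it as if it were both.

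Folding hides a slip's text until the slip is opened. It does not stop the person who opens it from drawing again, holding the slip for another patient, or finding the present patient ineligible. It also does not stop that person from counting what is left in a pool of known composition.

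Some entry decisions leave room for judgement, such as whether a patient communicates well enough. The exclusion criteria also allow inclusion up to one day after the reversal, when the operation and the early course may already be known. If such decisions can be made with an assignment in view, the groups may differ in prognosis before treatment starts. The planned analysis offers little protection: intention-to-treat is cited for attrition, and the stratified chi-square tests do not address unmeasured prognosis.

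**Working it through.** **Roles and safeguards**

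| Step | Who or what the plan names |
|---|---|
| Eligibility check and enrolment | Principal investigator |
| Case number | Principal investigator |
| Allocation | Principal investigator |
| Holder of the slips other than the enroller | Not specified |
| Sealed or numbered container | Not specified |
| Enrolment made final before the draw | Not specified |
| Log of draws, or a bar on redrawing | Not specified |

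**Inputs**

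- Pool of 30 slips, n = 15 per group (Sequence Generation).
- Planned sample of 60, 30 per group (Sample Size). The plan's one-sided formula reproduces this closely: 2 × 85.0914 × (1.645 + 1.645)² / (75.73 − 67.73)² = 28.8, so 29 per group against 30 stated. The present point does not depend on this figure.
- Assumption: drawing without replacement. The plan does not state it, but equal groups imply it.
- Assumption: a 30+30 pool for the 60 patients. The plan describes only the 30 slips.
- Assumption: a contrast of 4.6 h, which is half the plan's SD (0.5 × 9.2245 = 4.61), and twice that, 9.2 h.

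**Step 1: predictability.** The enroller guesses the group with more slips left and guesses at random when the counts are equal. Expected correct guesses are E = n + ½ × [4ⁿ / C(2n, n) − 1].

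- n = 15: 15 + ½ × (6.922 − 1) = 17.96 of 30, or 59.9%.
- n = 30: 30 + ½ × (9.749 − 1) = 34.37 of 60, or 57.3%.

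An exact recursion over all draw orders gives the same values. Chance alone gives 50%.

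**Step 2: certain draws.** Once one group's slips are used up, the rest are known. The expected number of such draws is 2n / (n + 1): 30/16 = 1.9 for n = 15 and 60/31 = 1.9 for n = 30.

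**Step 3: illustrative bias.** Suppose patients enrolled on a guess of one group have expected flatus time raised by s, those on the opposite guess have it lowered by s, and there is no shift when the counts are equal. Each correct guess widens the difference in means by s/n and each wrong guess narrows it by s/n. Expected correct minus wrong guesses is 2(E − n), so the spurious difference is D = 2s(E − n)/n.

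| Contrast between opposite guesses (2s) | 15+15 pool | 30+30 pool |
|---|---|---|
| 4.6 h (s = 2.3) | 4.6 × 2.961/15 = 0.91 h | 4.6 × 4.374/30 = 0.67 h |
| 9.2 h (s = 4.6) | 9.2 × 2.961/15 = 1.82 h | 9.2 × 4.374/30 = 1.34 h |

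Against the 8 h pilot difference, the first row is 8 to 11% and the second is 17 to 23%. These figures cover guessing from the count only. A redraw after the slip has been seen is not limited by guess accuracy.

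**The case against.** The strongest reply is that the draw is random, early draws from a well-mixed pool are close to even, and a tally is right only 57 to 60% of the time. That stands: predictability alone is a moderate threat. It does not answer the main weakness, which is that one person holds every role and no step is tamper-evident.

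Several stronger readings are tempting, and the documents do not support them.

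- **That the principal investigator hand-picks patients.** The plan uses the label purposive without naming a selector, and the label may mean no more than selection by criteria. On its own it bears on generalisability. It adds to bias between groups only if assignments can be foreseen or changed.
- **That every discretionary exclusion is the enroller's.** The bar on oral intake is the surgeon's decision, and several surgeons operate.
- **That the result would lean towards a favoured product.** Both products are described as current practice, and the hypothesis has no direction.
- **That a 4.6 h contrast produces a bias of 1.3 to 1.8 h.** Those values need shifts of +4.6 h and −4.6 h, a swing of 9.2 h. Nothing shows that an enroller could sort patients by expected flatus time to that degree.
- **That redraws would leave no record.** The plan does not say what is recorded or when the draw takes place relative to enrolment. The accurate statement is that this is not specified.

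The 30-slip text also matches the pilot's size and may describe only the pilot. No other procedure is given for the 60 patients, and the weakness is the same for either pool.

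**Conclusion.** The point holds as a design weakness. The procedure does not conceal assignments from the person who enrols. The statements that it gives unbiased allocation, that folding ensures blinding and that random assignment deals with selection bias are therefore not supported. A fixed equal pool is restricted randomization, not simple randomization.

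The guess rates (18 of 30, or 34.4 of 60) rest on drawing without replacement, and the second also on an assumed 30+30 pool. The bias figures, about 0.7 to 0.9 h or 1.3 to 1.8 h depending on the contrast, are scenarios and not estimates. The case for change rests mainly on the unseparated roles. No figure stated in the plan is wrong because of this point, and no misconduct is implied.

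**What to change.** - Before the first patient, an existing department member who neither enrols nor assesses outcomes shuffles the slips for the full planned sample and seals them in sequentially numbered opaque envelopes.
- The principal investigator enrols eligible patients consecutively, keeps a screening log that includes those not enrolled, and writes the case number in the log and on the next envelope before it is opened.
- An existing staff member who neither enrols nor records outcomes then opens the envelope. This should not be the ward doctor on duty, who collects the outcome data under Implementation.
- Delete the statement that folding ensures blinding. Describe the method as restricted randomization with a fixed equal allocation, and reword the selection-bias sentence under Blinding to rest on the concealment procedure.

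The cost is 60 envelopes, a short preparation session and a log. The principal investigator no longer draws the slip. No extra patients are needed and treatment is unchanged. One limit remains: if the principal investigator learns each assignment, a fixed pool of 60 can still be counted. Consecutive enrolment with the log is what restricts the use of that knowledge.

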- **Postoperative ileus:** Postoperative ileus is an abnormal pattern of slow or absent gastrointestinal motility in response to surgical procedures. It is measured as the absence of flatus/stool and inability to tolerate an oral diet within 3 days after surgery (34) (35).
- **Postoperative nausea and vomiting (PONV):** PONV is defined as documented postoperative nausea/emesis or administration of a rescue antiemetic (36).
- **Length of postoperative stay:** Defined as the time, in hours, from completion of reversal surgery to the time of discharge from the hospital (14).

HYPOTHESIS

There is a significant difference in the effect of chewing gum and honey on postoperative recovery and complications in ileostomy reversal.

MATERIALS AND METHODS

METHODS

Trial Design: Prospective single-blinded randomized controlled trial. Parallel design with allocation ratio 1:1 will be used. This manuscript is a protocol for the pilot RCT.

Participants: Patients presenting to the outdoor and ward of West Surgical Department with an Ileostomy and undergoing Ileostomy reversal surgery in the operation theatre.

Study Setting and Location: Male and Female Ward, West Surgical Department, Mayo Hospital, Lahore

Sample Size:

Due to deficiency of literature about the use of honey in gastrointestinal surgery and specifically intestinal anastomosis, it was decided that pretesting with a pilot study would be conducted to calculate the sample size. The overall sample size of 30 participants for the pilot trial was selected according to the Rule of Thumb for pilot trial sample size calculation. 15 participants in each group, i.e. Group A for chewing gum and Group B for honey, were allocated randomly using the lottery method. The primary outcome variable was time to pass flatus. The results of the pilot trial for the primary outcome variable showed that the mean time to pass flatus in Group A was 67.73 ± 8.481 hours and Group B was 75.73 ± 9.968 hours.

Outcome Variable	Group A		Group B		Population SD (σ)	Sample Size (n)
	Mean	SD	Mean	SD		
Bowel sounds	51.20	9.937	59.20	8.970	9.466	31
Time to pass flatus	67.73	8.481	75.73	9.968	9.254	29
Time to pass stools	100.80	11.632	119.47	12.994	12.332	10
Time for full feeds	79.47	10.239	93.33	11.178	10.719	13

The means and standard deviations of the pilot trial data was used to calculate the sample size using WHO Sample Size Calculator using the formula for hypothesis tests for two population means (one-sided test) as follows:

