Statistical analysis of the data will be carried out using IBM SPSS Statistics V26.0 for the Window program (IBM, Armonk, New York, USA). Qualitative variables such as gender, presence or absence of postoperative complications will be analyzed using frequencies and percentages. Quantitative variables such as age, length of postoperative stay, time to full feeds, time to bowel sounds, time to pass flatus and time to pass feces will be analyzed by calculating their mean and standard deviation. The data collected will be analyzed using descriptive statistics, such as frequencies, percentages, and means. Chi-Square test and logistic regression will be used to analyze the categorical variables whereas continuous variables will be analyzed using student t-test. Outcome data of the three groups will be compared to see the statistically significant difference, p-value of < 0.05 will be considered statistically significant. Outcome data will be stratified for age, gender, operative surgery, postoperative complications and post stratification chi square test will be applied. All qualitative data will be evaluated using

frequency tables. Any changes in the pre-operative and post-operative values will be calculated in absolute as well as percentages. The data will be explored using descriptive studies.

REFERENCES

2. de Gaay Fortman DPE, Kroon HM, Bedrikovetski S, Fitzsimmons TR, Dudi-Venkata NN, Sammour T. A snapshot of intraoperative conditions to predict prolonged postoperative ileus after colorectal surgery. *ANZ J Surg* [Internet]. 2022 Sep;92(9):2199–206. Available from: <http://www.ncbi.nlm.nih.gov/pubmed/35579059>

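### Operation type, age and gender are to be accounted for by a chi-square test that cannot adjust times in hours; the cost is precision, not validity

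*Combined protocol and SAP*

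**What the plan says.** **Who is eligible.** Inclusion Criteria: "Undergoing surgery involving reversal of an Ileostomy i.e., Loop Ileostomy, Double Barrel Ileostomy, Ileocolostomy or End Ileostomy".

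**How they are allocated.** Sampling Technique describes a lottery, "ensuring that the sample population is divided into the two groups equally and randomly regardless of their characteristics". Sequence Generation describes a single set of folded slips, half marked A and half B, with no separate set for operation or surgeon.

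**Surgeons.** Under Blinding: "Performance bias could not be eliminated due to different surgeons performing the ileostomy reversal surgery". No handling of surgeon is given there or later.

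**Analysis.** Sample Size states: "The primary outcome variable was time to pass flatus". It is measured in hours. In the Data Analysis Procedure, "continuous variables will be analyzed using student t-test", and "Chi-Square test and logistic regression will be used to analyze the categorical variables". Then: "Outcome data will be stratified for age, gender, operative surgery, postoperative complications and post stratification chi square test will be applied". Surgeon is not in that list. No linear model or pooled stratified estimate is named for the times.

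**The concern.** The plan names operation, age and gender as factors worth accounting for, then gives them a tool that cannot do so for its primary and co-primary outcomes. A chi-square test compares proportions. Unless hours are cut into categories, which is not planned, it cannot be run on time to flatus, bowel sounds or feces. Run within strata, it still gives no single adjusted difference in hours. If the sentence was meant for categorical outcomes only, the time outcomes have no stratified analysis at all. Either way, the comparison that carries the trial is an unadjusted t-test.

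Two things are at stake. If reversal type affects time to flatus, its share of the variance stays in the error term and widens the confidence interval. And in a trial of 60, one arm may by chance hold more of the slower operations, with no prespecified analysis to take that into account.

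The Blinding section also files surgeon differences under the wrong heading. Gum or honey starts 24 hours after surgery, so the operation and its surgeon come before study treatment. That is pre-treatment variation, not a difference in care caused by knowledge of the assigned group.

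**Working it through.** **Inputs from the protocol.** 30 per group; mean times to flatus 67.73 and 75.73 h, a difference of 8.00 h; SD 9.2245 h in the formula (plain average of the two pilot SDs) and 9.254 h in the table (pooled).

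**The plan's own figure.** One-sided 5%, 95% power: n = 2 × 85.0914 × (1.645 + 1.645)² / 8² = 28.8, so 29 per group. This matches the table and is one below the 30 per group adopted.

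**Assumed inputs.** The documents give neither the mix of operations nor the effect of type on flatus. I take 6 to 18 of 60 patients (10% to 30%) as non-loop, with an effect of 5 to 12 h. The pilot SD is taken to include variation between types. Slips are taken to be drawn without replacement, 30 A and 30 B overall.

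**Step 1: chance of imbalance.** The number of non-loop patients in one arm is hypergeometric. A 20-point gap is 6 patients, since 6/30 = 0.20.
- 6 of 60 non-loop: all six must fall in one arm, 2 × C(30,6)/C(60,6) = 2.4%.
- 12 of 60: 10.4%.
- 18 of 60: 15.8%.

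**Step 2: shift if it happens.** Shift = gap × effect: 0.20 × 5 = 1.0 h, up to 0.20 × 12 = 2.4 h, against the planned 8 h. The typical shift is smaller. The SD of the gap in proportions is 0.0781 (6 of 60) or 0.1193 (18 of 60), so one SD of shift runs from 0.0781 × 5 = 0.39 h to 0.1193 × 12 = 1.43 h.

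**Step 3: precision.** With p the non-loop proportion and d the effect, the share of variance is p(1 − p)d²/9.254², and the cut in standard error is 1 − √(1 − share).

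| Non-loop | Effect | Variance share | Cut in SE |
|---|---|---|---|
| 10% | 5 h | 0.026 | 1.3% |
| 10% | 12 h | 0.151 | 7.9% |
| 30% | 5 h | 0.061 | 3.1% |
| 30% | 8 h | 0.157 | 8.2% |
| 30% | 12 h | 0.353 | 19.6% |

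The unadjusted standard error is 9.254 × √(2/30) = 2.39 h. Adjustment would bring it to 2.36 h at the low end and 1.92 h at the high end. These figures ignore the degrees of freedom spent.

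**Step 4: validity and power.** Trials of 60 were simulated with four types in an assumed 50/20/15/15 mix, SD 9.2245 h and two-sided 5% tests. Type I error of the unadjusted t-test was 4.8% when type explained 10% of the variance and 5.4% when it explained 30%. Power for an 8 h difference, unadjusted against adjusted, was 91.0% against 92.0% at a 10% share, and 91.1% against 97.0% at 30%. By formula, two-sided power at 30 per group without adjustment is 91.9% (SD 9.2245) or 91.7% (SD 9.254).

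**The case against.** The best defence is that the plan does randomise, and that simple randomisation without strata is an accepted design. Imbalance under it is chance, and the t-test's standard error already includes it. If the pilot enrolled the same mix of operations, its SD, and so the sample size, already allow for it. Two-sided power is about 92% without adjustment, and the gain may be small. All of this stands.

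It limits what can be concluded. A reader might infer that mixing four operations biases the comparison or makes the p-value wrong. The documents do not support that: allocation is by lottery, and the simulated type I error stays near 5%. A reader might also infer from the Blinding sentence that nothing protects against surgeon differences. Randomisation does so on average; what is missing is any use of surgeon in the analysis. The documents do not show that the surgeon goes unrecorded either, because the case report form is not in the text reviewed.

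Nor does splitting the lottery by operation repair this by itself. If 18 non-loop patients draw from their own set of 60 slips, the chance of a gap of 6 or more is still 15.8%. With 40 slips it is 11.1%, and with 30 slips 6.0%.

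What the defence does not answer is that the plan chose these factors itself and gave them a test that does not fit its main outcomes.

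**Conclusion.** The point holds as a mismatch between the plan's intention and its method. For the time outcomes, operation, age and gender cannot be accounted for in the way the Data Analysis Procedure describes. The unadjusted t-test remains valid. The loss is precision, together with a chance shift in this trial's estimate that no planned analysis would address.

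The size rests on assumptions, since the documents give no operation mix and no effect of type. Over 10% to 30% non-loop and 5 to 12 h, the standard error falls by about 1% to 20% with adjustment, and a 20-point imbalance has probability of about 2% to 16%. At the low end the gain is negligible. The case for the change is that it is nearly free and acts on factors the plan already names.

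**What to change.** **Data Analysis Procedure.** For the time outcomes, replace the post-stratification chi-square test with one prespecified linear model of hours on group, reversal type (loop or other), age and gender. Define the operative factor as type of reversal. State before the data are seen whether this model or the t-test carries the conclusion.

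Do not use postoperative complications as an adjustment stratum. They arise after randomisation, and ileus is defined partly by absence of flatus or stool within 3 days. Stratifying on it would sort patients partly by the primary outcome.

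**Surgeon.** Record the operating surgeon, if the case report form does not already do so, and tabulate surgeon by group.

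**Blinding.** Keep the acknowledgement that different surgeons operate. Restate it as pre-treatment variation that randomisation balances on average, and remove the claim that it is performance bias that could not be eliminated.

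**Optional.** Separate slip sets by reversal type help only if each is made up in small balanced blocks. Because the principal investigator both enrols and allocates, small blocks also make the next slip easier to guess.

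**Cost.** One extra model in the SPSS package already planned, at most one form field, and a few degrees of freedom: 60 − 5 = 55 residual against 60 − 2 = 58 for the t-test.

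### The plan names one primary and two co-primary outcomes but no rule for which must be significant; it leans to flatus alone, yet leaves open a claim on any one of the three

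*Combined protocol and SAP*

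**What the plan says.** Three places bear on which outcome decides the trial.

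- **Sample Size** states: "The primary outcome variable was time to pass flatus". The total of 60 (30 per group) is justified by the pilot means and SDs for flatus only.
- **Outcome Measures** puts flatus alone under the primary heading. A second heading, "Co-primary Outcomes", holds time to bowel sounds and time to feces. Time to full feeds, pain, nausea and vomiting, and length of stay are secondary.
- **Follow-up** speaks of two tiers only: "The primary and secondary outcomes will be assessed at 8 hourly intervals".

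The Data Analysis Procedure assigns the t-test to continuous variables and sets a single criterion: "p-value of < 0.05 will be considered statistically significant". It gives no decision rule, testing order or multiplicity adjustment. The Hypothesis does not settle the matter, because it refers to recovery and complications as a whole: "There is a significant difference in the effect of chewing gum and honey on postoperative recovery and complications in ileostomy reversal".

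On sidedness, Sample Size cites the "formula for hypothesis tests for two population means (one-sided test", but the list of inputs under the formula prints 1.96 for the significance term, and the hypothesis has no direction.

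**The concern.** A co-primary label normally puts an outcome on the same footing as the primary one. With three outcomes at that level and no rule, the plan can be read in three ways: flatus alone decides, all three must be significant, or any one suffices. The first two hold the false-positive chance at or below 5%. The third does not. Because the text does not choose, the rule could be settled after the results are known, and a reader of the final report could not tell whether a positive finding on feces or bowel sounds alone was what the trial set out to test.

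**Working it through.** **Inputs.** From the pilot table in Sample Size: flatus 67.73 h against 75.73 h, difference 8.00 h, SDs 8.481 and 9.968, tabulated common SD 9.254; bowel sounds difference 8.00 h, common SD 9.466. The formula's input list gives a slightly different SD for flatus, 9.2245. Level 5%, power 95%, 30 per group. Correlations between the outcomes are not given and are assumed.

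**1. The plan's own sample size.** The formula is n = 2σ²(z₁₋α + z₁₋β)² / (μ₁ − μ₂)².

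- Flatus, one-sided z = 1.645: 2 × 9.254² × (1.645 + 1.645)² / 8² = 28.97, so 29 per group, as tabulated. SD 9.2245 gives 28.78, again 29.
- Bowel sounds, one-sided: 2 × 9.466² × (3.290)² / 64 = 30.31, so 31, as tabulated.
- Flatus with the printed 1.96: 2 × 9.254² × (1.96 + 1.645)² / 64 = 34.78, so 35 per group.

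The table was therefore computed one-sided. The printed 1.96 does not reproduce it. The 30 per group covers the 29 for flatus but not the 31 for bowel sounds, which supports reading flatus as the outcome the trial was built on.

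**2. False-positive chance under each reading, no true differences.**

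- Flatus alone: 5%.
- All three required: at most 5%, since it cannot exceed the chance for any single test.
- Any one suffices, independent tests: 1 − 0.95³ = 0.1426, or 14.3%.
- Any one suffices, correlated tests: for three normal test statistics with common correlation ρ and c = 1.96, the chance is 1 − ∫ φ(z) [Φ((c − √ρ z)/√(1−ρ)) − Φ((−c − √ρ z)/√(1−ρ))]³ dz.

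| Assumed correlation | Two-sided chance of at least one false positive |
|---|---|
| 0 | 14.3% |
| 0.5 | 12.5% |
| 0.7 | 10.9% |
| 0.9 | 8.4% |
| 0.99 | 6.0% |

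Correlation shrinks the excess over 5% but does not remove it at any value short of 1.

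**3. Flatus power at 30 per group.** The standard error is 9.254 × √(2/30) = 2.389, and 8 / 2.389 = 3.348.

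- Normal formula, one-sided: Φ(3.348 − 1.645) = 95.6%. Two-sided: Φ(3.348 − 1.96) = 91.7%.
- Noncentral t, 58 degrees of freedom: 95.2% one-sided, 90.9% two-sided.

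Two-sided 95% power needs 35 per group by the plan's normal formula, or 36 by the noncentral t (95.1%).

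**The case against.** The best answer is that the plan already points to flatus. It is the only outcome under the primary heading, it is called the primary outcome variable, and it alone justifies the 60 patients. That stands, and it is why the inflated error rate is conditional. It does not explain the second heading. If flatus alone decides, the co-primary label is a mistake, and removing it is the fix proposed here.

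A second answer is that Trial Design says "This manuscript is a protocol for the pilot RCT", and the randomisation text describes 30 slips. Error control matters less in a pilot. However, Sample Size reports the pilot's results as finished and uses them to size a 60-patient trial with a significance test and a power target. The point applies to that trial.

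Two stronger readings are tempting, and the documents do not support either.

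- A reader might infer that the trial runs at a 14.3% false-positive rate. No section states an any-one rule, and 14.3% also needs three bowel-recovery times in the same patient to be uncorrelated. It is a ceiling on the least supported reading.
- Follow-up says "The final assessment point will be till the time of discharge or a maximum of 5 days/144 hours postoperatively", and 5 days is 120 h. With a pilot honey mean of 119.47 h to stool, a reader might infer that a 120 h limit would leave many feces times unobserved. The pilot data speak against such a limit having been used there. If none of 15 values exceeded 120 h, the total shortfall below 120 h would be 15 × 0.53 = 7.95 h. The largest possible SD, with one patient carrying all of it, is √[(7.42² + 14 × 0.53²)/14] = 2.05 h. The reported SD is 12.994 h, so the pilot recorded times beyond 120 h, and nothing says the 60-patient trial would use a shorter limit. Treatment starts at 24 h, and 24 + 5 × 24 = 144, which may be what was meant. The wording needs reconciling, but no loss of power can be claimed from it.

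**Conclusion.** The concern holds as an unresolved decision rule that should be fixed; it does not show that the planned error rate is wrong. On the reading the plan favours, the false-positive chance is 5%. On the any-one reading that the co-primary label leaves open, it is about 8% to 13% two-sided for correlations of 0.9 to 0.5. Those figures assume approximately normal test statistics with one common correlation, which the documents do not supply.

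The sidedness conflict is a separate matter and does not cause the multiplicity gap. The stated 95% power for flatus holds only for one-sided tests. With two-sided tests at 30 per group it is about 91% by the noncentral t, or about 92% by the plan's normal formula, taking the pilot difference and SD as true.

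**What to change.** 1. In Outcome Measures, name time to flatus as the sole primary outcome, drop the co-primary heading, and list time to feces and time to bowel sounds as secondary. In the Data Analysis Procedure, state that the trial's conclusion rests on flatus at the 5% level.
2. If confirmatory claims on feces or bowel sounds are wanted, fix their order in advance and test each at 5% only after flatus is significant, stopping at the first non-significant result. Requiring all three, or a Holm or Bonferroni adjustment, would also control the error. The fixed order is suggested because it matches the plan's own sizing and costs flatus no power.
3. State whether tests are one-sided or two-sided, and bring the formula label, the 1.96 and the hypothesis into line. If two-sided, restate the flatus power as about 91%.
4. Reconcile the 5 days with the 144 hours in Follow-up.

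The cost is a few sentences and no extra patients. The downside of the ordering is that neither feces nor bowel sounds can support a positive claim if flatus fails, although feces showed the larger pilot difference (119.47 − 100.80 = 18.67 h). Restating the power costs nothing; keeping 95% two-sided would take 35 to 36 per group, depending on the method.
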